4.6 Study Patients

4.6.1 Disposition of Patients

Patient disposition will be summarized by treatment group for all patients by Stage 1 and Stage 2 combined, Stage 3 alone and by stages 1, 2 and 3 combined. Important protocol deviations and analysis sets will be tabulated using the safety analysis set (see [Section 4.5](#)). The number and percentages of patients will be presented for the following categories:

- All enrolled
- Randomised to study treatment
- Not randomised to study treatment (and reason)
- Received study treatment
- Did not receive study treatment (and reason)
- Completed study treatment
- Discontinued from study treatment (and reason)
- Completed study
- Prematurely withdrawn from study (and reason).

The number of patients recruited in each country and each centre will be presented by treatment group and total.

Additional listings and summaries on patients affected by the COVID-19 pandemic will also be presented.

4.6.2 Protocol Deviations

Important protocol deviations are defined as those deviations from the protocol likely to have a large impact on the interpretation of any analysis based on addressing the primary and secondary objectives of the trial.

The following general protocol deviation categories will be programmatically derived from the electronic case report form (eCRF) data. These deviations will be reviewed and assessed on a case-by-case basis by the study team to determine importance. Deviations considered to be important will be listed and discussed in the CSR as appropriate. All decisions on importance will be made ahead of database lock and will be documented prior to the analysis being conducted. Deviations will include, but are not limited to:

- Patients who deviate from inclusion /exclusion criteria per the Clinical Study Protocol (CSP) (Deviation 1).
- Patients who fail to sign the correct informed consent form, except the genetic informed consent form, before randomisation (Deviation 2).
- Patients whose baseline safety assessments as per CSP are missing (Deviation 3).
- Patients who received prohibited medications during the study (Deviation 4). Refer to the CSP Section 6.5 for those medications that are detailed as being ‘excluded’ from permitted use during the study. This will be used as a guiding principle for the physician review of all medications prior to database lock.
- Patients who don’t have a baseline biopsy (Deviation 5).
- Patients who don’t have an on-treatment biopsy (Deviation 6).
- Patients randomised who received an incorrect dose to that which they were randomised to (Deviation 7).
- Received AZD9833 and had an on-treatment biopsy more than 12 hours after last AZD9833 dose (Deviation 8).

- Pre- or on-treatment FFPE samples contain ≤ 100 tumour cells (Deviation 9).
- No on-treatment FFPE blocks provided (Deviation 10).
- Received AZD9833 and had an on-treatment biopsy without a minimum of 5 consecutive dosing days (Deviation 11).
- A minimum of 2 slides are not available from either the baseline or on-treatment biopsy (Deviation 12).

The following will be checked for analysis purposes and will not be included as part of the deviations to be recorded in the protocol deviations log during the study:

- Patients randomised but who did not receive any study treatment (Deviation 13).
- Patient vomits on the day of PK sampling and within 8 hours of AZD9833 dosing (Deviation 14). These will be reviewed on a case-by-case basis to determine whether any exclusion from the PK analysis set is deemed necessary.
- Non-invasive tumour biopsy scorings (Deviation 15).

Patients who received the wrong treatment at any time will be included in the analysis set as described in [Section 4.5](#). During the study, decisions on how to handle errors in treatment dispensing (with regards to continuation/discontinuation of study treatment or, if applicable, analytically) will be made on an individual basis with written instruction from the study team leader and/or statistician.

Important protocol deviations will be listed and summarised by randomised treatment group. Important protocol deviations related to COVID-19 will be summarised separately.

Table 4: Summary of Deviations and Actions

Deviation	Action
Deviation 13	Exclusion from the Safety Analysis Set
Deviations 5, 6, 8-11 and 12	Patient becomes non-evaluable and to exclusion from the PD analysis set
Deviation 15	Exclusion of non-invasive tumour biopsy scorings from analysis
Other/further deviations	Will not lead to patients being excluded from the analysis sets described in Section 4.5 unless the deviation is considered to impact upon pharmacodynamic data. Non-evaluable patients will be replaced.

A per-protocol analysis excluding patients with specific important protocol deviations is not planned, however a sensitivity analysis may be performed on the key PD endpoints if $> 10\%$ of patients in any treatment group have any other significant deviation deemed to affect the primary endpoint which haven't already led to exclusion from the PD analysis set.

The need for such a sensitivity analysis will be determined following review of the protocol deviations ahead of database lock and will be documented prior to the analysis being conducted.

In addition to the programmatic determination of deviations above, other study deviations captured from the eCRF module for inclusion/exclusion criteria will be tabulated and listed. Any other deviations from monitoring notes or reports will be reported in an appendix to the CSR.

A full list of protocol deviations can be found in the study-specific Protocol Deviation Specification.

4.6.3 Demographic and Other Baseline Characteristics

No formal statistical analysis of baseline data will be provided for this study. Demographic and other baseline disease characteristics will be summarised and listed by treatment group for all patients by

Stage 1 and Stage 2 combined, Stage 3 alone, and by Stages 1, 2 and 3 combined in the safety analysis set as follows:

- Demographics (age [years], age group [<50; 50-59; 60-69; ≥ 70], sex [only female patients are expected in this study], race and ethnicity).
- Patient characteristics at baseline (height [cm], weight [kg], and body mass index [BMI] [kg/m²]).
- Previous non-breast related treatment modalities.
- Disease characteristics at baseline (Eastern Cooperative Oncology Group [ECOG] performance status, primary tumour location (breast), histology type, tumour grade, tumour stage /AJCC stage, receptor status [ER/PgR/Ki67/HER2]).
- Tumour, node and metastasis (TNM) classification at baseline.
- Neurological assessment (listed only).
- Time from diagnosis of primary breast cancer to randomisation.

4.7 Medical and Surgical History

Disease related medical history and relevant surgical history will be coded using the Medical Dictionary for Regulatory Activities (MedDRA). All disease related medical history (past and current) will be listed and the number and percentage of patients with any disease related medical history will be summarised for the safety analysis set by system organ class (SOC) and preferred term (PT).

All relevant surgical history will be listed and summarised similarly.

4.8 Concomitant Medications and Treatment

Information on any treatment that the patient is receiving at the time of enrolment and all concomitant treatments given up to 28 days after discontinuation of study treatment, with reasons for the treatment will be recorded in the eCRF. Any form of anti-cancer treatments, investigational agents, disallowed medications and radiotherapy should not be given while the patient is on study treatment. See Section 6.5 of CSP for a list of prohibited medications and anti-cancer treatments.

Treatments (including surgery), received prior to, concomitantly, or post-treatment will be coded using the World Health Organisation (WHO) Drug Dictionary (WHODD) Anatomical Therapeutic Chemical (ATC) classification codes. Concomitant medications will be summarised for the safety analysis set by ATC classification codes.

For the inclusion in prior and/or concomitant medication or treatment summaries, incomplete medication or treatment start and stop dates will be imputed as detailed in [Section 4.3.2.1](#) and [Section 4.3.2.2](#).

- Prior medications are those taken prior to study treatment with a stop date prior to first dose of study treatment.
- Concomitant medications are those with a stop date on or after the first dose date of study treatment (and could have started prior to or during treatment).
- Post treatment medications are those with a start date after the last dose date of study treatment.

The following summaries will be produced:

- Cancer therapies prior to this study.
- Disallowed concomitant medications (as identified during physician review described in [Section 4.6.2](#), deviation 4).

- Allowed concomitant medications.
- Concomitant procedures.
- Post-discontinuation cancer therapy.

The number and percentage of patients who took any previous cancer treatments will be summarised by therapy class (i.e. immunotherapy, hormonal therapy, cytotoxic chemotherapy, systemic therapy and other). The prior cancer (non-breast) therapy regimens will be listed.

Listings of prior, concomitant and post treatment medications, will be provided; and the timing of the medications will be marked clearly as ‘prior’, ‘concomitant’ or ‘post’.

4.9 Curative intent surgery

Curative intent surgery details will be listed. If the reasons for no surgery/delay in surgery for a patient is not collected on CRF, data management lead will provide the reasons in a separate MS Excel sheet after contacting study sites, which will subsequently be reviewed and approved by study medical monitor. This excel sheet will be used for curative intent surgery listings and excel sheet will be filed in the TMF at the end of the study.

4.10 Pharmacodynamic Evaluation

Biopsy samples will be sectioned and assessed for tumour content. Pathologist scoring for ER, PgR and Ki-67 expression will be carried out at a contracted external good clinical practice (GCP) accredited laboratory. Sections will be scored for ER, PgR and Ki-67 expression in tumour by a contracted independent pathologist who will be blinded to treatment groups.

For patients where more than one tumour block has been provided for a single timepoint, a weighted mean score based on the percentage (%) of tumour cells in each section will be used as the score for that timepoint. Non-invasive tumour biopsy scorings will be excluded from the PD summaries and listings.

For example: If $i=1, 2, 3 \dots n$ is the number of tumour blocks provided for a single patient for a particular tumour assessment visit; and the sample has corresponding percentage tumour tissues t_i and H-scores h_i (total H-score for ER and PgR expressions, and percentage tumour cells with positive nuclei for Ki-67 expression), then the weighted mean score for that patient for that particular visit is calculated as follows:

$$\sum_{i=1}^n \left(\frac{t_i}{\sum_{i=1}^n t_i} \right) h_i \quad \text{where } i=1,2, 3 \dots n$$

The weighted mean score will be used as is in the analyses, where the score will be rounded off to the nearest integer before presenting in the summary tables.

Pathology scoring will be summarised and listed by treatment group for all patients by Stage 1 and Stage 2 combined, Stage 3 alone, and by Stages 1, 2 and 3 combined by actual treatment group and by visit.

The receptor status will be listed for safety analysis set by ER and PgR total H-score, Ki67 labelling index, and HER2 IHC positive staining.

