4.2 General Data Presentation Characteristics

The data from all countries and stages will be combined and reported together. Stage 1 and Stage 2 data combined and Stage 3 data alone will also be reported separately. All data will be summarised by treatment group and timepoint.

Continuous data will be summarised using descriptive statistics (the number of patients [n], mean, standard deviation [SD], median, 25th and 75th percentiles [where appropriate], minimum and maximum unless otherwise stated). For log-transformed data it is more appropriate to present geometric mean (gmean), geometric coefficient of variation (CV), median, minimum and maximum.

For continuous data, the mean, median and gmean will be rounded to one additional decimal place compared to the original data. The SD and geometric CV will be rounded to two additional decimal places compared to the original data. Minimum and maximum will be displayed with the same accuracy as the original data. The maximum number of decimal places reported will be four for any summary statistic.

Categorical data will be summarised in terms of the number of patients providing data at the relevant time point (n), frequency counts and percentages. Percentages will not be presented for zero counts. Unless otherwise stated, percentages will be calculated using the number of patients included in the analysis set for that treatment group as denominator and presented to one decimal place.

Confidence intervals (CIs), when presented, will generally be constructed at the 2 sided 80% level. CIs will be presented to one additional decimal place compared to the original data.

For safety, PD, and PK endpoints the last observation prior to the first dose of study treatment will be considered the baseline measurement unless otherwise specified. For assessments on the day of first dose where time is not captured, a nominal pre-dose indicator, if available, will serve as evidence that the assessment occurred prior to first dose. Assessments on the day of first dose where neither time nor a nominal pre-dose indicator are captured will be considered prior to first dose if such procedures are required by the protocol to be conducted before first dose.

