4.10.2 Ki-67 Labelling Index

Ki-67 labelling index will be assessed and expressed as the average percentage of tumour cells with counted positive nuclei, following the International Ki-67 in Breast Cancer Working Group Recommendations. Ki-67 labelling index will be scored by increments of 1% and can range from 0 – 100. When the number of tumour cells per section for a counted biopsy is less than 100 tumour cells, then the Ki-67 labelling index is not reported and NE will be stated.

The secondary pharmacodynamic biomarker variables of change from baseline in Ki-67 labelling index after 5 to 7 days of AZD9833 treatment for Stage 1 and Stage 2; and after 12 to 15 days of AZD9833 treatment for Stage 3 will be listed and summarised based on the PD analysis set (see Section 4.5).

It is expected that the distribution of the Ki-67 labelling index data will not be normally distributed (Robertson et al 2013, Robertson et al 2020b), hence Ki-67 labelling index data will be naturally log-transformed before being analysed. Ki-67 will be analysed similarly to ER and PgR, using a parametric ANCOVA on natural log transformed data. Values equal to zero on the original scale will be set to one (1), and one will be added to the corresponding baseline/biopsy day labelling index value before natural log transformation. Log transformed baseline score will be included as a covariate, and day of biopsy and treatment group included as fixed effects. The estimated treatment effect together with 80% CIs for all treatment durations (5 to 7 consecutive days of AZD9833 treatment for stage 1 and stage 2, and 12 to 15 consecutive days of AZD9833 treatment for stage 3), as per the model fitted will be back transformed to the original scale for reporting. For listings, original values will be reported.

Sensitivity analyses for Ki-67 labelling index

If necessary, sensitivity analysis will be conducted on a subset of the PD analysis set by excluding:

- Any patients who are considered to be HER2 positive by central assessment.
- Any patients with a Ki-67 labelling index < 5% from their pre-treatment biopsy.
- Any patients with an ER H-score < 10 on their pre-treatment biopsy.
- Any patients with an ER H-score < 10 on their pre-treatment biopsy or any patients with a Ki-67 labelling index < 5% from their pre-treatment biopsy.

If considered necessary, further cuts and sensitivity analyses may be performed.

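### The log-scale zero rule for Ki-67 covers only exact zeros, so an unrounded multi-block score between 0% and 1% can be analysed as stronger suppression than 0%

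*SAP*

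**What the plan says.** Three rules meet here.

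- **Scoring grid (SAP 4.10.2).** "Ki-67 labelling index will be scored by increments of 1% and can range from 0 – 100". A single block therefore scores a whole number.
- **Several blocks at one timepoint (SAP 4.10).** The blocks are combined into a mean weighted by tumour percentage. The formula names Ki-67 explicitly, with the block score being the "percentage tumour cells with positive nuclei for Ki-67 expression". On use, the plan says "The weighted mean score will be used as is in the analyses", whereas for tables "the score will be rounded off to the nearest integer before presenting in the summary tables".
- **Zeros before the log (SAP 4.10.2).** Ki-67 is analysed "using a parametric ANCOVA on natural log transformed data". Beforehand, "Values equal to zero on the original scale will be set to one (1"), and for the same patient "one will be added to the corresponding baseline/biopsy day labelling index value before natural log transformation".

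The log analysis of ER and PgR in SAP 4.10.1 uses the same kind of zero rule. Neither section has a rule for values above 0 and below 1.

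**The concern.** The zero rule suits whole-number scores. Averaging across blocks takes scores off that grid, and the rule then has a gap. A true 0 is pulled up to 1, while a 0.4 is logged as it stands, although 0.4 shows more staining than 0. A patient with some residual proliferation is then credited with deeper suppression than a patient with none, and very small fractions become very large negative log ratios.

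Low on-treatment scores are plausible in this trial. SAP 4.13 calls Ki-67 the key secondary endpoint for Stage 3 and illustrates an 80% fall; from a baseline of 5% such a fall ends at 5 × 0.20 = 1%. The estimates at stake are the back-transformed Ki-67 changes and their confidence intervals, which under SAP 4.2 "will generally be constructed at the 2 sided 80% level".

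**Working it through.** **Inputs.** From the SAP: unrounded weighted mean in the analyses (4.10); 1% grid, exact-zero rule and log ANCOVA (4.10.2); Ki-67 half-width of 0.312 on the log scale with 24 per group, and the illustrated −80% with interval (−85%, −73%) (4.13). Assumed: baseline Ki-67, B, which the SAP does not give. A range of 1 to 50 is shown.

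**1. The plan's own figure.** 0.20 × exp(−0.312) − 1 = −85.4% and 0.20 × exp(+0.312) − 1 = −72.7%. These round to the stated (−85%, −73%), so 0.312 is a sound yardstick.

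**2. Can a score between 0 and 1 occur?** Yes. Two blocks scored 0% and 1% with tumour weights 60 and 40 give (60 × 0 + 40 × 1)/100 = 0.4.

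**3. What the model sees.** For an on-treatment score x and baseline B:

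- x = 0 is analysed as the ratio 1/(B+1);
- x > 0 is analysed as the ratio x/B.

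The order reverses when x/B < 1/(B+1), that is, when 0 < x < B/(B+1).

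| Assumed B | Reversal below | Change analysed for 0% | Change analysed for 0.4% |
|---|---|---|---|
| 1 | 0.500 | −50.0% | −60.0% |
| 5 | 0.833 | −83.3% | −92.0% |
| 10 | 0.909 | −90.9% | −96.0% |
| 20 | 0.952 | −95.2% | −98.0% |
| 50 | 0.980 | −98.0% | −99.2% |

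For 0.4 the reversal needs B/(B+1) > 0.4, so B > 0.67. It therefore holds at every baseline of 1% or more. On whole numbers the order is right: at B = 20, a score of 1 gives 1/20, or −95.0%, and 0 gives 1/21, or −95.2%.

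**4. On the ANCOVA scale.** The model adjusts for log baseline with a slope β rather than using the ratio directly. The difference between a score of 0.4 and a score of 0 is then ln(0.4) + β × ln((B+1)/B). For β of 0, 0.5 and 1 and B of 1, 5 and 20 it runs from −0.22 to −0.92. The reversal does not depend on the slope.

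**5. Effect on a group mean.** At B = 20 the log ratios are ln(0.4/20) = −3.912 and ln(1/21) = −3.045, a difference of −0.867. One such patient among 24 shifts the unadjusted log mean by −0.867/24 = −0.036, and 0.036/0.312 = 12% of the half-width. A more extreme score of 0.05 (blocks of 0% and 1% weighted 95:5) has a log ratio of −5.991. The shift is then (−5.991 + 3.045)/24 = −0.123, or 39% of the half-width.

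**The case against.** The strongest reply is that the problem is narrow. It needs more than one block at the timepoint and invasive scores averaging below about 1%. The SAP gives no count of such patients, and there may be very few. With a score of 0.4 the shift is a small part of the planned precision, and only much smaller fractions act as strong outliers. Ki-67 is a secondary endpoint in an exploratory estimation study. SAP 4.10.2 allows further sensitivity analyses, and a non-parametric approach if the transformed model fits badly. All of this stands and limits the consequence. None of it repairs the rule: those analyses are optional, and dropping baselines below 5% leaves the reversal at B = 10 or 20 untouched.

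A reader might also infer that the Ki-67 tables and the Ki-67 model use different data, because scores are rounded for one and not for the other. The SAP does not support that. The rounding sentence in 4.10 can be read as a display rule. SAP 4.2 takes the percentage change of a log-transformed variable from the ratio calculated on the log scale, and nothing says that changes or geometric means are computed from rounded scores. A numerical gap between table and model would need that unstated assumption. Display rounding also plays no part in the reversal, which comes from the unrounded mean meeting a rule for exact zeros.

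**Conclusion.** The point holds as a minor defect of SAP 4.10.2 read with 4.10. For multi-block patients, any on-treatment Ki-67 score strictly between 0 and B/(B+1) is analysed as stronger suppression than 0%, and no other section corrects this. For 0.4% against 0% the distortion is 10.0 percentage points at an assumed baseline of 1%, 5.1 at 10%, 2.8 at 20% and 1.2 at 50%. The direction needs no assumption beyond a baseline of at least 1%; the sizes rest on the assumed baselines. The 12% figure rests on B = 20, one affected patient in 24 and an unadjusted mean. The total effect on the trial's estimates cannot be stated, because the number of affected patients is not given. The same gap exists in the ER and PgR log analysis but matters less on a 0 to 300 scale. No disagreement between tables and model is shown; the purpose of the rounding is only left unclear.

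**What to change.** - **SAP 4.10.2:** apply the existing adjustment to all values below 1 instead of only to values equal to zero. Any such score is set to 1 and 1 is added to the paired value before the log. At B = 20, scores of 0 and 0.4 then both give 1/21, or −95.2%, and a score of 1 gives −95.0%, so the order is right.
- **SAP 4.10.1:** use the same wording for the log analysis of ER and PgR.
- **SAP 4.10:** say that rounding applies to displayed values only, and that changes and summary statistics are computed from unrounded scores. This is a clarification, not the correction of a shown error.

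The cost is a short wording change in each of the three sections, with no new data. The one loss is that scores below 1% are no longer told apart. Adding 1 to every baseline and on-treatment value would also restore the order (at B = 20: −95.2%, −93.3% and −90.5% for 0, 0.4 and 1). But it alters every patient's log ratio, for example moving a score of 1 from −95.0% to −90.5%, so the narrower change is preferable. It should be made before database lock, because SAP 3.5 has the study team unblinded throughout and a later choice about near-zero scores would be made with the results in view.
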